5.1. Safety/Efficacy Population

The safety population will include all subjects who receive any AP-PA02 or placebo. Subjects will be analyzed according to treatment received. This population will be used for all analyses of safety endpoints and for the presentation of subjects in all subject listings including subject disposition.

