6.1. General Methods

All analyses and summaries will be produced using Statistical Analysis System (SAS®) version 9.4 or higher. All SAS programs used to generate analytical results will be developed and validated according to SYNH programming standards and SAS validation procedures. Summaries will be presented by cohort/dose group and overall unless otherwise specified. Each active treatment group will be labeled in the outputs by its Phage Cocktail and estimated total protein per total plaque-forming units (PFU) for each dose for the SAD cohorts and the total dose per treatment course for the MAD cohorts. Additionally, pooled placebo will be presented.

The naming convention for the listings include:

- Cohort 1 Single Ascending Dose (SAD): 3-Phage Cocktail, AP-PA02 (1E10 PFU single dose)
- Cohort 1 Single Ascending Dose (SAD): 3-Phage Cocktail, Placebo
- Cohort 2 Single Ascending Dose (SAD): 3-Phage Cocktail, AP-PA02 (3E10 PFU single dose)
- Cohort 2 Single Ascending Dose (SAD): 3-Phage Cocktail, Placebo
- Am5 SAD: Single Ascending Dose (SAD): 3-Phage Cocktail, AP-PA02 (9E10 PFU single dose)
- Am5 SAD: Single Ascending Dose (SAD): 3-Phage Cocktail, Placebo
- Am5 MAD: Multiple Ascending Dose (MAD): 3-Phage Cocktail, AP-PA02 (1E10 PFU/dose x 3 doses/day x 3 days)
- Am5 MAD: Multiple Ascending Dose (MAD): 3-Phage Cocktail, Placebo
- Cohort 3 Multiple Ascending Dose (MAD): 5-Phage Cocktail, AP-PA02 (5.75E10 PFU/dose x 2 doses/day x 5 days)
- Cohort 3 Multiple Ascending Dose (MAD): 5-Phage Cocktail, Placebo
- Cohort 4 Multiple Ascending Dose (MAD): 5-Phage Cocktail, AP-PA02 (1.5E11 PFU/dose x 2 doses/day x 10 days)
- Cohort 4 Multiple Ascending Dose (MAD): 5-Phage Cocktail, Placebo
- "Screen Failures" if applicable

The naming convention for the tables and figures include:

- Cohort 1: 3-Phage (1E10 PFU SD)
- Cohort 2: 3-Phage (3E10 PFU SD)
- Cohort 3: 5-Phage (5.75E10 PFU/dose x 2 doses/day x 5 days)
- Cohort 4: 5-Phage (1.5E11 PFU/dose x 2 doses/day x 10 days)
- Pooled Placebo

Pooled Placebo group in the tables and figures will include Protocol Amendment 5 subjects.

Results for subjects assigned to either of the following dose groups will be included in the listings only:

- Am5 SAD: Single Ascending Dose (SAD): 3-Phage Cocktail, AP-PA02 (9E10 PFU single dose)
- Am5 MAD: Multiple Ascending Dose (MAD): 3-Phage Cocktail, AP-PA02 (1E10 PFU/dose x 3 doses/day x 3 days)

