7.1. Subject Disposition and Withdrawals

A summary table will be produced detailing the number of subjects screened and screen failed, the number and percentage of all subjects in each analysis population, subjects who completed or discontinued study treatment, subjects who completed or who prematurely discontinued the study. In addition, reasons leading to discontinuation from study and study treatment discontinuation will be summarized for each cohort and overall. A listing of subject disposition will also be provided.

Screened subjects are defined as all subjects with a non-missing informed consent date and screen failures are defined as all subjects who sign the informed consent but are not enrolled into the study.

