The eight respiratory symptom items will be rescored, summed, and converted to a 0 to 100 scale using the scoring guidelines of the Cystic Fibrosis Respiratory Symptom Diary (CFRSD) and Chronic Respiratory Infection Symptom Scale (CFRSD-CRISS), Version 2.0, 8 September 2016. The CFRSD-CRISS will not be calculated if more than one item response is missing. Scoring of the emotional and activity impact items is still under development and will not be summarized. The rescaling schema and conversion table are provided in [Appendix 15.2](#). CFRSD severity score and absolute changes from baseline will be summarized for visits 2 through 6/EOS for SAD cohorts, and visits 2 through 8/EOS for MAD cohorts using summary statistics.

For SAD Visits 3, 4, 5, 6 and MAD Visits 6, 7, 8, 9 for Cohort 3 and MAD visits 11, 12, 13, and 14 for Cohort 4 under Protocol Version 6, there will be multiple days of diary data. The average daily score will be calculated for these multiple days and presented for a single visit corresponding to the Schedule of Assessments in Appendix 1 of the Protocol. Results for Daily Symptom Diary will be grouped to a single study visit if it occurs on the day of the study visit up until the day before the next visit is performed. For example, if a subject's Visit 3 occurs on Study Day 3, and Visit 4 occurs on Study Day 8, then the Daily Symptom Diary results for Study Day 3, 4, 5, 6, and 7 will be averaged and summarized for Visit 3.

This document is confidential.

9. Safety

The population used for safety analyses will be the Safety Population. Safety will be assessed on the basis of treatment emergent adverse event (TEAE), dose-limiting toxicities (DLTs), vital signs, laboratory assessments, immunogenicity, electrocardiogram (ECG) parameters, and physical examinations.

All safety information will be provided in subject listings.

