9.2. Adverse Events

An overall summary of TEAEs will be provided, including the number and percentage of subjects who experience at least one of the following will be summarized by dose cohort and overall for each study part:

- TEAEs
- Serious TEAEs
- TEAEs related to study drug
- TEAEs related to study device
- TEAEs related to study procedure
- Serious TEAEs related to study drug
- Serious TEAEs related to study device
- Serious TEAEs related to study procedure
- TEAEs leading to permanent withdrawal of study drug
- TEAEs related to study drug leading to permanent withdrawal of study drug
- TEAEs of interest
- DLTs
- TEAEs with Grade 1 (Mild) as Worst Severity
- TEAEs with Grade 2 (Moderate) as Worst Severity

This document is confidential.

- TEAEs with Grade 3 (Severe) as Worst Severity
- TEAEs with Grade 4 (Life-Threatening) as Worst Severity
- TEAEs leading to death

The number and incidence of events will be provided in the overall summary table by dose cohort and overall for each study part.

TEAEs are defined as an adverse event that was not present prior to administration of the first dose of study drug and subsequently presented after the first dose, or any exacerbation occurring after first dose of an event that was present prior to the first dose.

All AEs will be listed by subject and chronologically by date of AE onset, and by study part, dose group, and subject. This listing will include all data collected in the eCRF and the coded variables. AE dates will be listed as recorded in the eCRF. AEs will be classified by System Organ Class (SOC) and Preferred Term (PT) using MedDRA Version 23.0. Subjects are counted only once within each SOC and PT. TEAEs will be presented by descending frequency by SOC and PT.

Further, the following TEAE summaries will be provided and summarized by dose cohort and overall for each study part:

- Any TEAEs overall and by SOC and PT
- Serious TEAEs, overall and by SOC and PT
- Study Drug-related TEAEs overall and by SOC and PT
- Study Device-related TEAEs overall and by SOC and PT
- Study Procedure-related TEAEs overall and by SOC and PT
- Serious TEAEs related to Study Drug, overall and by SOC and PT
- Serious TEAEs related to Study Device, overall and by SOC and PT
- Serious TEAEs related to Study Procedure, overall and by SOC and PT
- TEAEs by worst severity, overall and by SOC and PT
- Study Drug-related TEAEs by maximum severity, overall and by SOC and PT

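### SAP section 6.1 drops both Amendment 5 AP-PA02 groups from every table but keeps Amendment 5 placebo subjects, contrary to the Safety Population rule in sections 5.1 and 9

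*SAP*

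**What the plan says.** Section 5.1 defines the analysis set without exception: "The safety population will include all subjects who receive any AP-PA02 or placebo". It then fixes its use: "This population will be used for all analyses of safety endpoints and for the presentation of subjects in all subject listings including subject disposition". The opening of section 9 repeats the point: "The population used for safety analyses will be the Safety Population".

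Section 6.1 sets out two column schemes. The listings scheme includes two Amendment 5 regimens, a single-dose group and a multiple-dose group, each with an AP-PA02 and a placebo arm. The scheme for tables and figures has only Cohorts 1 to 4 and Pooled Placebo. Two rules follow. On placebo: "Pooled Placebo group in the tables and figures will include Protocol Amendment 5 subjects". On the two Amendment 5 AP-PA02 groups (9E10 PFU as a single dose; 1E10 PFU three times a day for three days): "Results for subjects assigned to either of the following dose groups will be included in the listings only".

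Section 7.1 asks the disposition table for "the number and percentage of all subjects in each analysis population". Section 9.2 says of TEAEs: "The number and incidence of events will be provided in the overall summary table by dose cohort and overall for each study part". Section 11, on changes from the protocol's planned analysis, is marked as not applicable.

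**The concern.** Sections 5.1 and 9 cannot both be followed together with section 6.1. A subject dosed with AP-PA02 under Amendment 5 belongs to the population on which every safety analysis is to be run, yet that subject's results may appear in no table or figure.

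The omission also depends on arm. Of the subjects treated under the same amendment, those on placebo are tabulated and those on AP-PA02 are not. The primary endpoints of both study parts are the incidence and severity of TEAEs (section 4.1), and incidence is read from tables, not listings. An SAE or DLT in an Amendment 5 AP-PA02 subject would be missing from the TEAE, SAE and DLT tables, while the same event in an Amendment 5 placebo subject would add to the placebo count. Pooled Placebo would also contain subjects whose active counterparts have no column.

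**Working it through.** There is no stated figure to reproduce; section 3.6 says the sample size is not based on power. The check compares the text and adds simple arithmetic.

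**1. The rules side by side**

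| Subject dosed under Amendment 5 | Sections 5.1 and 9 | Section 6.1 |
|---|---|---|
| AP-PA02 | In the Safety Population, so in all safety analyses | Listings only |
| Placebo | In the Safety Population, so in all safety analyses | Listings, and tables and figures through Pooled Placebo |

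The two sources agree for placebo and conflict for AP-PA02. No analysis set defined in section 5 matches the set of subjects tabulated. Section 12.2.3 requires each display to name its population and section 12.2.4 requires that population's size in the column headings, so a table labelled Safety Population would omit some of its members.

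**2. Which exposures are left out** (regimens from section 6.1)

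- Amendment 5 single dose against the highest tabulated single dose (Cohort 2): 9E10 / 3E10 = 3.
- Amendment 5 multiple-dose course: 1E10 × 3 × 3 = 9E10 PFU. No other multiple-dose group received the 3-phage cocktail.
- Cohort 3 course (5-phage): 5.75E10 × 2 × 5 = 5.75E11 PFU.
- Cohort 4 course (5-phage): 1.5E11 × 2 × 10 = 3.0E12 PFU.

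The tabulated 3-phage columns therefore stop at a single 3E10 PFU dose and hold no multiple-dose subjects. The highest exposure in the study, in Cohort 4, is tabulated.

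**3. How many subjects**

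Planned Cohorts 1 to 4 (section 3.6) give 3 + 3 + 3 + 15 = 24 on AP-PA02 and 1 + 1 + 1 + 5 = 8 on placebo, a ratio of 3:1. The number of Amendment 5 subjects is not stated. The two rows below are assumptions that apply the same 3:1 ratio and take Cohorts 1 to 4 at planned size:

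| Assumed Amendment 5 subjects (active + placebo) | Tabulated active : placebo | Active subjects omitted |
|---|---|---|
| 3 + 1 | 24 : 9 = 2.67 : 1 | 3 / (24 + 3) = 11.1% |
| 6 + 2 | 24 : 10 = 2.4 : 1 | 6 / (24 + 6) = 20.0% |

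In both rows the tabulated total is smaller than the Safety Population and every missing subject is on AP-PA02. Without actual counts and events, no effect on TEAE incidence can be derived.

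**4. Totals**

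Read literally, the listings-only rule also keeps these subjects out of the overall columns. The disposition table remains unclear, because section 7.1 asks it to count everyone in each analysis population while section 6.1 provides no column for these subjects.

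**The case against.** The best defence is that section 5.1 defines membership and section 6.1 governs display. The listings-only rule names both groups and stands beside the placebo rule, so it reads as a deliberate specific rule that qualifies a general one. The SAP is based on protocol version 6.0, whose four-cohort design does not contain these groups, and the protocol may explain why. All summaries are descriptive, and Pooled Placebo already mixes single- and multiple-dose subjects and both cocktails, so it was never matched to any one active column. Every adverse event is still listed by study part, dose group and subject. Finally, no numerical effect has been shown, and a cross-reference, a reason and a footnote with the number excluded would remove the conflict in wording.

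Part of this stands. The listings keep the individual data visible, section 6.1 is open about its rule, the literal wording largely settles the overall columns, and the size of the effect is unknown.

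It does not remove the problem. A reason based on protocol version 6.0 would apply equally to the Amendment 5 placebo subjects, who are kept. The section 6.1 remark on early closure of the study concerns which outputs may be needed, not which arm to leave out. Descriptive tables still report incidence, and a listing does not. A footnote would disclose the one-sided omission but leave it in the primary-endpoint tables.

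**Conclusion.** The concern holds. Section 6.1 conflicts with sections 5.1 and 9, and it removes treated subjects from the primary-endpoint tables in one arm only, without a stated reason. This should be fixed.

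The size can be described but not calculated. The tables lose the 3-phage single dose that is three times the highest one tabulated, and the only 3-phage multiple-dose group. The 11.1% and 20.0% shares of omitted active subjects rest on assumed Amendment 5 enrolment and on planned sizes for Cohorts 1 to 4; they are illustrations only. The gap concerns the 3-phage product and not the highest exposure in the study, and the listings limit the harm.

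**What to change.** Replace the listings-only rule in section 6.1:

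- **Disposition, exposure and all AE, SAE and DLT tables:** include the Amendment 5 AP-PA02 subjects, in one or two added columns, and state that they count in the overall figures.
- **By-visit laboratory, vital-sign, ECG and spirometry tables:** either include these subjects, or exclude Amendment 5 AP-PA02 and placebo subjects alike, with the reason and the number excluded in a footnote.
- **Consistency:** align sections 5.1, 7.1 and 9 with the revised rule. Section 6.1 selects these subjects by the group to which they were assigned, whereas section 5.1 analyses by treatment received; the safety tables should use one basis.

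The cost is a change of SAP wording and one or two columns in a limited set of tables. The data are already destined for the listings, so nothing new is collected. If the added columns hold few subjects, that calls for cautious reading or a single combined column.

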6.2. Key Definitions

6.2.1. Baseline

Unless otherwise specified, baseline is defined as the last non-missing observation prior to the first dose of AP-PA02. Screening visit will be considered baseline if non-missing and the nominal visit 'Baseline' is missing. The Baseline Visit will be scheduled between Day -7 and Day -1 (inclusive) relative to Visit 1 Day 1 for all cohorts. Screening evaluations cannot be combined with evaluations performed as part of the Baseline Visit.

6.2.2. Study Day

The day of first dose of study drug administration is defined as study Day 1. Subsequent days are numbered consecutively (Day 2, Day 3, etc.). Prior to the day of first dose of study drug administration, study days are numbered sequentially with negative values (i.e., Day -1, Day -2, etc.). There is no Day 0.

6.3. Missing Data

In general, missing data will not be imputed. All analyses will be based on observed cases. Sections 6.3.1 and 6.3.2 note the situations where missing data will be imputed.

6.3.1. Handling of Missing Dates/Months/Years for Prior/Concomitant Therapies

If the medication cannot be classified into concomitant or prior status due to incomplete start and/or stop date, the rules below will be applied for the classification.

For start date,

- If the year and month are observed but the day is missing, the first day of the month will be used unless month and year are the same as month and year of first dose date then impute using the day of first dose date
- If the year is observed but the month and day are missing, the first day of the year, 01 Jan, will be used unless year is the same as first dose date then the first dose date will be used
- If the start date is completely missing, the medication will be considered concomitant unless the stop date is before study drug administration
- If the start and stop dates are both completely missing, a therapy will be considered concomitant.

For end date,

- If the year and month are observed but the day is missing, the last day of the month will be used unless month and year are the same as month and year of last dose date, then impute the last dose date
- If the year is observed but the month and day are missing, the last day of the year, 31 Dec, will be used unless year is the same as last dose date then the last dose date will be used

This document is confidential.

- If the end date is completely missing, if medication is still ongoing, then missing end date is not supposed to be imputed. If the medication is not ongoing and the start date is prior to first dose date, the end date will be imputed using 1st dose date.
- If both start and end dates are completely missing, medication will be considered concomitant.

The original partial or missing date will be shown in listings for all prior and concomitant medications.

6.3.2. Adverse Events Dates

For AEs with incomplete dates, the following rules will be used to impute start and/or stop dates for the sole purpose of determining if an AE is treatment-emergent. Imputed dates will not appear in the data listings.

For partial start dates:

- If the month and year of AE onset are provided but day is missing
 - If the month and year match the month and the year of the date of first dosing administration, then the date of first dosing administration will be used and the AE will be considered treatment-emergent.
 - Otherwise, the first day of the month will be used.
- If the year of AE onset is provided, but the month and day are missing
 - If the year matches the year of the first dosing administration, then the date of first dosing administration will be used.
 - Otherwise, 01 Jan will be used.
 - If the stop date is not missing and the imputed onset date is after the stop date, then the stop date will be used.
 - If the onset date is completely missing and the stop date is on or after the date of first dose, the event will be considered a TEAE.
 - If both onset date and stop date are missing, the event will be considered a TEAE. Partial stop dates will not be imputed in this instance.

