4.1. Primary Endpoint

4.1.1. Part 1: SAD Evaluation

The primary endpoints of Part 1 of the trial are the incidence and severity of treatment-emergent adverse events (TEAEs), occurring from Day 1 pre-dose through the End of Study (EOS) Visit

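### SAP 6.3.2 declares an adverse event with a missing onset day in the first-dose month treatment-emergent even when its recorded stop date is before the first dose

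*SAP*

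**What the plan says.** Section 6.3.2 imputes incomplete AE dates "for the sole purpose of determining if an AE is treatment-emergent". For partial onsets it has two branches.

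- **Month and year known, day missing.** If they match the first dose, "then the date of first dosing administration will be used and the AE will be considered treatment-emergent". Otherwise the first of the month is used. Neither sub-bullet looks at the stop date.
- **Only the year known.** "If the year matches the year of the first dosing administration, then the date of first dosing administration will be used". Otherwise 1 January is used. No statement about treatment-emergent status is attached.

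Three more bullets are printed at the sub-level of the year-only branch. The first is the stop-date guard: "If the stop date is not missing and the imputed onset date is after the stop date, then the stop date will be used". The second confers TEAE status on certain events whose onset is wholly missing, and begins: "If the onset date is completely missing and the stop date is on or after the date of first dose, the event will be considered". The third makes an event a TEAE when both dates are missing.

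Section 9.2 gives the definition: "TEAEs are defined as an adverse event that was not present prior to administration of the first dose of study drug" and that then appears after it, or a worsening after the first dose of something already present. It also repeats that a missing onset counts as treatment-emergent only if the stop date is missing or is not before the first dose.

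**The concern.** An event that ended before the first dose cannot be treatment-emergent under 9.2: it neither appeared nor worsened after dosing. The month-and-year branch nevertheless assigns that status outright. A wholly missing onset with a pre-dose stop date does not trigger the TEAE rule, and a year-only onset with a pre-dose stop date is moved back to that stop date. The most informative kind of partial date is therefore the one that gets the wrong answer, which argues against deliberate conservatism.

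Incidence and severity of TEAEs are the primary endpoints of both parts (4.1.1 and 4.1.2), and most active groups are very small, so a single wrong flag would show in the tables. If the relationship or severity field were also blank, the missing-value rules in 9.2 would further count the event as drug-related or severe.

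**Working it through.** The SAP gives no figure to reproduce. The check is whether its rules, applied in order, return the right flag.

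**Inputs.** The rules are those of 6.3.2, and the standard is the definition in 9.2. Planned active group sizes are 3, 3, 3 and 15 for Cohorts 1 to 4 (section 3.6). The test case uses assumed dates: first dose 15 March 2022, onset March 2022 with day unknown, stop 10 March 2022. By 9.2 this event is not a TEAE.

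**Two points the text leaves open.** (a) The guard may apply only to year-only onsets, as printed, or to all partial onsets. (b) The treatment-emergent statement may bind in its own right, or only describe what follows from the imputed date. Where it does not bind, I took an event as treatment-emergent if its final imputed onset is on or after the first-dose date.

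**Month-and-year branch:**

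| Guard applies to | Statement binds? | Imputed onset | Flag |
|---|---|---|---|
| Year-only onsets | Yes | 15 March | TEAE (wrong) |
| Year-only onsets | No | 15 March | TEAE (wrong) |
| All partial onsets | Yes | 10 March | TEAE (wrong; onset precedes first dose) |
| All partial onsets | No | 10 March | Not a TEAE (right) |

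**Year-only branch, same event.** The imputed onset of 15 March is after the stop of 10 March, so the guard sets it to 10 March. The event is not a TEAE under any of the four combinations.

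The correct flag in the month-and-year branch needs two things the text does not say: that the guard reaches this branch, and that it overrides the explicit statement.

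**Weight of one wrong flag.** The change in a group's TEAE incidence, when the affected subject has no other TEAE, is 100/n percentage points:

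- n = 3: 100/3 = 33.3 points
- n = 15: 100/15 = 6.7 points

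If the subject has another TEAE, overall incidence does not change; only the term-level, event-count or severity entries could.

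**The case against.** The strongest reply is that the printed indentation cannot be trusted. The two bullets after the guard concern onsets that are wholly missing, which cannot be sub-cases of a branch that requires the year to be known. The guard's own wording speaks of the imputed onset date without restriction. All three bullets may well be general rules whose nesting was lost. On that footing the test event's onset becomes 10 March. Since the dates are imputed solely to decide treatment-emergent status, a guard that moved the date but left the flag alone would have no purpose. The statement in the month-and-year branch would then merely describe the result of using the first-dose date, and would lapse once the guard replaced it. The definition in 9.2 points the same way.

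Much of this stands. The guard may be general, the authors probably meant a pre-dose stop date to exclude the event, and the four combinations above are not equally likely, so three wrong results out of four is not a probability. The text still says in so many words that the event will be treated as treatment-emergent, and nothing withdraws it. A programmer following it literally would produce an onset before the first dose together with a TEAE flag.

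It is also fair that the AE summaries are descriptive, the sample size is not based on power, and the listings show dates as recorded. A misflagged event could be spotted there, but the tables would still contain it.

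**Conclusion.** Wrong as written. For a missing onset day in the first-dose month, 6.3.2 assigns treatment-emergent status without condition. With a stop date before the first dose, the result either contradicts 9.2 outright or, if the guard is general, sets a pre-dose onset against a TEAE flag.

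The trigger is narrow, and the SAP gives no frequency for it. The 33.3 and 6.7 points are the effect of one affected active subject with no other TEAE at the planned group sizes. They are not an expected bias.

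Two stronger conclusions are tempting and unsupported. A reader might infer that the plan certainly puts pre-dose events into the primary endpoint. It does so on the literal text, but the guard's unclear scope leaves room for a programmer to reach the right answer, and no such event is known to exist. A reader might also infer that many events are affected, because those shortly before dosing usually share its month. If first doses spread evenly over a 30-day month, an event starting 1 to 7 days earlier falls in that month with probability 1 − 1/30 = 96.7% down to 1 − 7/30 = 76.7%. That is the chance of a month match alone. It says nothing about how often the onset day is missing and the stop date is before dosing, so it is not a misclassification rate.

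**What to change.** In section 6.3.2:

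1. Delete the treatment-emergent clause from the month-and-year branch, leaving only the imputation of the first-dose date.
2. Move the stop-date guard to the top level and say that it applies to every partial onset date. Move the two bullets on wholly missing onsets to the same level.
3. Add that an AE whose stop date precedes the first dose is not a TEAE. This should cover a complete stop date and a partial one that is unambiguously before the first dose. Use the stop date as the imputed onset only when it is complete, so that an incomplete date is never replaced by another.
4. State that in all remaining cases the flag follows from the final imputed date, with an onset imputed to the first-dose date counted as treatment-emergent. This keeps the intended conservative handling where the stop date is missing or is not before the first dose.

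With these changes the test event gets an onset of 10 March and is not a TEAE, which agrees with 9.2 and with the year-only branch. The cost is a few lines of SAP text and one condition in the AE dataset derivation. No new data are needed.
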